8.0 Study Drug Exposure and Compliance

8.1 Study Drug Exposure

The duration of exposure to study drug in M13-538 will be summarized for the Open-Label Treated Population by the following groups:

1. Upadacitinib 6 mg BID/15 mg QD

This includes upadacitinib 6 mg BID or 15 mg QD exposure from subjects who never titrated, as well as the upadacitinib 6 mg BID or 15 mg QD exposure prior to dose titration for subjects who titrated (censored at the time of up titration to 12 mg BID/30 mg QD).

2. Upadacitinib 12 mg BID/30 mg QD

This includes upadacitinib 12 mg BID or 30 mg QD exposure for subjects who titrated up (censored at the time of down titration to 6 mg BID/15 mg QD for subjects who titrated up and back down).

3. Upadacitinib 6 mg BID/15 mg QD post down titration

This includes upadacitinib 6 mg BID/15 mg QD exposure after down titration for subjects who titrated up and back down.

4. Any upadacitinib

This includes any upadacitinib exposure in Study M13-538.

The first three exposure groups are mutually exclusive in terms of exposure, and the three groups combined is represented by the fourth group.

The duration of exposure to study drug will be summarized for each exposure group as specified above, with the number of subjects, mean, standard deviation, median, minimum and maximum values. In addition, the number and percentage of subjects exposed to study drug will be summarized for the following cumulative duration intervals.

Open-label exposure:

- ≥ 6 months
- ≥ 12 months
- ≥ 18 months
- ≥ 2 years
- ≥ 2.5 years
- ≥ 3 years
- ≥ 4 years
- ≥ 5 years

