9.0 Efficacy Analysis

9.1 General Considerations

Long-term efficacy analysis will be performed on the Open-Label Treated Population by the treatment group sequences as defined below:

1. Upadacitinib never titrated (6 mg BID/15 mg QD),
2. Upadacitinib titrated up and not down (6 mg BID/15 mg QD to 12 mg BID/30 mg QD), and
3. Upadacitinib titrated up and down (6 mg BID/15 mg QD to 12 mg BID/30 mg QD and then back down to 6 mg BID/15 mg QD).

No statistical tests will be conducted; only descriptive statistics and confidence intervals will be provided. All data will be summarized based on As Observed data (defined in Section 9.1.1).

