9.1.1 Definition of Missing Data Imputation

As Observed (AO)

The AO analysis will not impute values for missing evaluations. All observed data will be used in the analysis. The AO analysis will be applied to long-term efficacy analysis.

Mixed Model Repeated Measures (MMRM) and Generalized Linear Mixed Model (GLMM)

The repeated measure analysis will be conducted using mixed model including As Observed measurements at all visits. MMRM will be used for continuous endpoints and GLMM will be used for binary endpoints. The mixed models will include the categorical fixed effects of treatment, visit and treatment-by-visit interaction. Prior RCT study will also be included as a fixed factor in the model. For the MMRM analysis of change from baseline in continuous endpoints, the baseline measurement will be included as a continuous fixed covariate. The categorical fixed effect of subject's discontinuation status may also be included in the model as appropriate. Unstructured, Toeplitz, compound symmetry, or other covariance structures may be considered.

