9.2 Long-Term Efficacy Analysis

Assessments to evaluate long-term efficacy will be analyzed for the following measures at Weeks 6, 12, 24, 36, 48, 60, 72, 84, 96 and every 12 weeks until Week 312.

- ACR20/50/70 response rates;
- Change from baseline in individual ACR components;
- Change from baseline in DAS28 (CRP);
- Change from baseline in CDAI and SDAI;
- Proportion of subjects achieving LDA and proportion of subjects achieving CR based on DAS28 (CRP), CDAI and SDAI criteria;
- Change from baseline in Patient Reported Outcomes, including FACIT-Fatigue Scale, RA-WIS, and EQ-5D;

Analyses will be based on As Observed (AO) data. Descriptive statistics will be provided for each treatment group sequence in the Open-Label Treated Population as defined in Section 9.1. These include the number of observations, mean, standard deviation, and 95% CI for continuous endpoints; and frequencies and percentages with 95% CI using normal approximation for binary endpoints. In addition, longitudinal analysis will be

performed using MMRM or GLMM as described in Section 9.1.1 for all endpoints for treatment sequences 1 and 2. Point estimates and 95% CI from the model will be provided. Plots over time will be provided.

Table 1 below provides the overview of the long-term efficacy analysis to be performed on different endpoints.

Table 2. Summary of Long-Term Efficacy Analysis

Measure of Interest	Analysis Method
Binary endpoints: 
 • ACR20 at each visit • ACR50 at each visit • ACR70 at each visit • LDA based on DAS28 (CRP) at each visit • LDA based on CDAI and SDAI at each visit • CR based on DAS28 (CRP) at each visit • CR based on CDAI and SDAI at each visit 	
 • Point estimate and 95% CI of the response rate for each treatment sequence • Point estimate and 95% CI of the response rate using GLMM model for treatment sequences 1 and 2 • Plots over time (for ACR responses and LDA/CR based on DAS28 and CDAI) • Imputation: AO • Population: open-label treated population

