10.0 Safety Analysis

10.1 General Considerations

Safety analyses will include reporting of adverse events, laboratory, and vital signs measurements in open-label treatment period only. Safety analyses will be carried out using the Open-Label Treated Population, which includes all subjects who received at least one dose of open-label study medication.

Long-term safety analyses include reporting of AE rate adjusted by cumulative exposure, mean change from baseline in laboratory parameters and vital sign variables, and frequency of potentially clinically significant laboratory and vital signs values.

The treatment-emergent adverse event (TEAE) rate per 100 patient-years of exposure will be presented by the exposure groups defined in Section 8.1, namely

1. Upadacitinib 6 mg BID/15 mg QD
2. Upadacitinib 12 mg BID/30 mg QD
3. Upadacitinib 6 mg BID/15 mg QD post down titration
4. Any upadacitinib

Listing of subjects with TEAEs by SOC and PT will be provided. Frequency tables and listings of subjects meeting criteria for potentially clinically significant vital sign values and for potentially clinically significant laboratory values will be provided by the exposure groups defined in Section 8.1.

Mean changes from baseline in all continuous laboratory parameters and vital signs variables at each visit will be summarized by the treatment group sequences defined in Section 9.1, namely

1. Upadacitinib never titrated (6 mg BID/15 mg QD),
2. Upadacitinib titrated up and not down (6 mg BID/15 mg QD to 12 mg BID/30 mg QD), and
3. Upadacitinib titrated up and down (6 mg BID/15 mg QD to 12 mg BID/30 mg QD and then back down to 6 mg BID/15 mg QD).

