10.3.2 Assessment of Mean Change from Baseline in Clinical Laboratory Values

Analyses of mean change from baseline in continuous hematology, chemistry, and urinalysis variables which are measured longitudinally will be performed by visits and by treatment group. For each change from baseline analysis, the following summary statistics will be presented for each treatment group sequence: sample size, baseline mean, visit mean, and the mean, standard deviation, and median of the changes from baseline.

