10.3.3 Assessment of Shift from Baseline in Clinical Laboratory Variables

The baseline and post-baseline laboratory observations will be categorized as Grade 1, Grade 2, Grade 3, and Grade 4 according to OMERACT criteria (Rheumatology Common Toxicity Criteria v.2.0). For creatine phosphokinase and creatinine NCI CTC criteria will be used.

For each laboratory variable, shift tables will be generated that cross tabulate the subjects as deemed appropriate by treatment sequence:

- Category of the baseline value versus category of the final value.
- Category of the baseline value versus maximum category.
- Category of the baseline value versus minimum category.

Note that the minimum/maximum category is used, rather than the category of the minimum/maximum value. The two may be different due to variation in the reference range.

No statistical tests will be performed for this analysis.

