10.4.2 Analysis of Long-Term Vital Signs

Mean changes from Baseline to post-baseline visits will be summarized with the baseline mean, the visit mean, change from baseline mean, standard deviation, and median. The number and percentage of subjects meeting the criteria for potentially clinically significant vital sign values will be summarized.

A listing of all subjects with any vital sign values meeting the criteria for potentially clinically significant vital signs will be provided. For each of these subjects, the whole course of the respective parameter will be listed.

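### The modelled efficacy curve for up-titrated subjects leaves out every visit of anyone whose dose is later reduced

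*SAP*

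**What the plan says.** SAP 9.1 defines three subject-level sequences: never titrated; raised and not reduced; and "Upadacitinib titrated up and down (6 mg BID/15 mg QD to 12 mg BID/30 mg QD and then back down" to the starting level. It gives no date cut and no rule that splits a subject's visits before and after a reduction.

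SAP 9.1.1 says of the model: "The repeated measure analysis will be conducted using mixed model including As Observed measurements at all visits". SAP 9.2 gives by-visit descriptive statistics for all three sequences, but the longitudinal analysis is "performed using MMRM or GLMM as described in Section 9.1.1 for all endpoints for treatment sequences 1 and 2". SAP Table 2 repeats this.

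SAP 8.1 treats the same event by time. Exposure group 2 holds higher-dose exposure "censored at the time of down titration to 6 mg BID/15 mg QD for subjects who titrated up and back down", and adverse event rates follow those exposure groups (SAP 10.1).

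The sequence grouping is also used for some safety summaries. SAP 10.1 states: "Mean changes from baseline in all continuous laboratory parameters and vital signs variables at each visit will be summarized by the treatment group sequences". SAP 10.3.3 uses it for laboratory shift tables.

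Under Protocol 5.1, the dose may be raised from Week 6, for example when CDAI exceeds 10. It may be reduced for safety or tolerability (an adverse event or a toxicity threshold) and, since Amendment 5, at the investigator's discretion.

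**The concern.** Whether a subject belongs to sequence 2 or 3 is known only once the full dose record is available. A Week 24 value from someone raised at Week 12 is in the model or out of it depending on a decision that may come years later. The modelled sequence 2 curve is thus conditional on never being reduced, and it discards observed higher-dose data.

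The MAR argument in SAP Appendix D does not cover this, because these visits are excluded by definition and are not missing. Long-term efficacy is part of the primary objective (SAP 4.1). A reader could take the modelled curve as the course of everyone who needed the higher dose, and no planned model shows that.

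**Working it through.** **1. Who is in the model.** Only sequences 1 and 2 are modelled, all visits of those subjects are used, and anyone ever reduced is in sequence 3. A reduced subject therefore contributes no visit to any MMRM or GLMM. The SAP states no figure for this analysis (no power, margin or test), so there is nothing to reproduce.

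**2. Visits lost.** SAP Table 1 has 27 post-baseline visits (Week 6, then every 12 weeks from Week 12 to Week 312, with no Week 18 window and none skipped otherwise).

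| Reduction at | Scheduled visits at or before it, all outside the model |
|---|---|
| Week 48 | 5 of 27 |
| Week 96 | 9 of 27 |
| Week 156 | 14 of 27 |
| Week 240 | 21 of 27 |

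**3. Size at visits before any reduction.** Let f be the share of up-titrated subjects later reduced, p2 the result in sequence 2, p3 the earlier result in sequence 3, and d = p2 − p3. Then sequence 2 minus all up-titrated = p2 − [(1 − f)p2 + f·p3] = f·d. The documents give neither f nor d. Over assumed values, in percentage points and with either sign possible:

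| f | d = 0 | d = 10 | d = 20 |
|---|---|---|---|
| 5% | 0 | 0.5 | 1 |
| 10% | 0 | 1 | 2 |
| 20% | 0 | 2 | 4 |
| 30% | 0 | 3 | 6 |

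**4. What a reader can recover.** SAP 9.2 plans n, mean and SD, or counts, for each sequence, so descriptive rows 2 and 3 can be pooled. Example: 80 subjects at 70% and 20 at 50% give (56 + 10)/100 = 66%, with 95% CI 66 ± 1.96 × √(0.66 × 0.34/100) × 100 = 56.7% to 75.3%, against 70% for sequence 2 alone. Pooling mixes visits before and after reduction. It cannot rebuild the model estimates, because sequence 3 is never modelled.

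**5. Would the alternatives do better?** Simulation with assumed inputs: 200,000 up-titrated subjects, 27 visits, between-subject variance 0.6, residual variance 0.4, no dropout. Reduction is possible from the second visit, with a logistic per-visit hazard set to give f. The target is the mean of all up-titrated subjects on the higher dose. The MMRM is maximum likelihood with unstructured covariance. Absolute error in SD units for f = 10%, 20%, 30%, with a reduction odds ratio of 2.72 per SD of the current value:

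| Estimate | Week 48 | Week 312 |
|---|---|---|
| Sequence 2 as planned | 0.06, 0.12, 0.19 | 0.06, 0.12, 0.19 |
| Combined, censored, by-visit mean | 0.01, 0.01, 0.02 | 0.06, 0.12, 0.18 |
| Combined, censored, MMRM | at most 0.003 | at most 0.003 |

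- With odds ratio 1.65, the sequence 2 error falls to between 0.03 and 0.10. With odds ratio 1, there is no error beyond simulation noise.
- If reduction depends on the subject's underlying level (odds ratio 2.72 per SD), sequence 2 is off by 0.07, 0.15 and 0.23 at Week 48. The censored MMRM is off by at most 0.02 at Week 312.
- The version regardless of reduction differs from the target at Week 312 by about f × the change after reduction: 0.03, 0.06, 0.09 for an assumed change of 0.3 SD.

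**6. Week 6.** The analysis window is Days 2 to 64 and takes the visit nearest Day 43 (SAP 5.3). A scheduled visit may be 7 days early (Protocol 5.1), and unscheduled visits can include joint counts, laboratory tests and vital signs (Protocol Table 2). A subject raised at a Day 36 visit and seen again on Day 45 has distances of 7 and 2 days from target, so the Day 45 value, on 12 mg BID, is used as Week 6.

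**The case against.** The case for leaving the SAP alone is substantial.

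- No tests are planned, no decision rests on these estimates, and the sequence labels say exactly who is in each group. This stands, and it limits the point to a suggested improvement.
- Restricting the model to sequences 1 and 2 looks deliberate, since the SAP's own summary of changes records it. That is fair, but the SAP gives no reason for it.
- The protocol's grounds for reduction are safety, tolerability and investigator discretion, with no efficacy trigger. An odds ratio of 2.72 per SD of an efficacy value is an assumption, and with no association there is no shift. This stands, and neither size nor direction can be claimed.
- SAP 8.1 divides person-time and SAP 9.1 describes trajectories, so they need not match. Agreed: SAP 8.1 shows only that the reduction date is available and that censoring at it is already accepted practice here.
- Censoring does not repair late by-visit means. At Week 312 the censored mean is almost as far off as sequence 2. The near-zero error of the censored MMRM owes much to assumptions that suit it, with reduction driven by observed values and no dropout. The real study discontinues subjects for inadequate joint response (Protocol 5.1, 5.4.1). This stands and shapes the fix.

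**Conclusion.** The point holds for the planned models. The MMRM/GLMM curve for sequence 2 describes subjects who were raised and never reduced, and it omits the pre-reduction visits of the rest. Its size is f x d, with both unknown: 0 to 6 percentage points over the ranges shown, in either direction, and possibly negligible. The reading rests on the sequence wording and on the absence of any time cut in SAP 9.1.

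Four stronger conclusions are tempting but not supported:

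- That the curve flatters the higher dose. No document gives the direction or the number of reductions.
- That reduced subjects vanish from the efficacy results. Sequence 3 keeps its descriptive rows, and Protocol 8.1.5.2 plans observed-case efficacy on the whole analysis set.
- That the safety analysis is compromised. Adverse event rates, potentially clinically significant values and liver criteria use the exposure groups. Laboratory and vital sign mean changes and laboratory shift tables do carry the same condition, but rows 2 and 3 can largely be pooled: "the following summary statistics will be presented for each treatment group sequence" (SAP 10.3.2), and these include sample size, mean and SD. For vital signs, pooling also needs n, which SAP 10.4.2 does not list.
- That every Week 6 value is on 6 mg BID. Nearly all should be, but the window rule allows exceptions.

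**What to change.** Keep all planned outputs and make two additions to SAP 9.2.

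1. One supplementary MMRM/GLMM with sequences 2 and 3 as a single up-titrated group, with visits censored at down-titration using the date SAP 8.1 already needs. Add the same model regardless of later reduction as a sensitivity analysis.
2. Footnotes stating that:
   - sequence 1 is selected on never up-titrating, which is partly an efficacy criterion (CDAI above 10 may prompt an increase);
   - the combined group includes 6 mg BID visits before up-titration, among them nearly all Week 6 values;
   - the censored version assumes that censored visits can be predicted from earlier ones.

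Do not present a censored by-visit mean as correcting late visits. Extra laboratory and vital sign versions are optional; showing n in the vital sign tables would be enough to allow pooling of means.

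The cost is SAP wording, programming and one extra set of model outputs, with no new data. Neither version is a pure higher-dose estimate: both include visits before up-titration, and the second also includes visits after reduction.

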9.1.1 Definition of Missing Data Imputation

As Observed (AO)

The AO analysis will not impute values for missing evaluations. All observed data will be used in the analysis. The AO analysis will be applied to long-term efficacy analysis.

Mixed Model Repeated Measures (MMRM) and Generalized Linear Mixed Model (GLMM)

The repeated measure analysis will be conducted using mixed model including As Observed measurements at all visits. MMRM will be used for continuous endpoints and GLMM will be used for binary endpoints. The mixed models will include the categorical fixed effects of treatment, visit and treatment-by-visit interaction. Prior RCT study will also be included as a fixed factor in the model. For the MMRM analysis of change from baseline in continuous endpoints, the baseline measurement will be included as a continuous fixed covariate. The categorical fixed effect of subject's discontinuation status may also be included in the model as appropriate. Unstructured, Toeplitz, compound symmetry, or other covariance structures may be considered.

